9 DATA ANALYSIS

Data will be handled and processed according to the Contract Research Organization's Standard Operating Procedures, which are written based on the principles of GCP.

9.1 Statistical Methods

The methodology presented below is a summary of the more detailed analysis plan that will be presented in the Statistical Analysis Plan (SAP). The SAP will be finalized before the database is locked and unblinded for Cohort 2. Any changes to the methods described in the final SAP will be described and justified in the clinical study report.

All statistical processing will be performed using SAS® (Version 9.4) unless otherwise stated. No interim efficacy analyses are planned.

Descriptive statistics will be used to provide an overview of the efficacy, safety and pharmacokinetic results. For categorical parameters, the number and percentage of subjects in each category will be presented. The denominator for percentage will be based on the number of subjects appropriate for the purpose of analysis. For continuous parameters, descriptive statistics will include n (number of subjects), mean, standard deviation (SD), median, minimum, and maximum.

P-values of less than 0.05 will be considered statistically significant based on a two-sided test unless otherwise specified.

9.1.1 Determination of Sample Size

A sample size of 24 per arm (72 total) will provide 80% power to detect a difference of 23% in the mean percent change from baseline in TPSS x target plaque area (cm^2) between the ARQ-151 cream and the matching vehicle arms, with a standard deviation for the change of 25%. This is based on a one-way analysis of variance (ANOVA) at the $\alpha = 0.025$ significance level. With a 16% dropout rate, the sample size for the study would be increased to 84 subjects.

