8.6 Randomization

Cohort 1: Cohort 1 is an open label single dose application of ARQ-151 cream 0.5% to 25 cm² of psoriatic plaque(s) in up to eight (8) subjects. Cohort 1 subjects may enroll in Cohort 2 if the eligibility criteria for Cohort 2 are met.

Cohort 2: Subjects will apply ARQ-151 cream 0.5% or ARQ-151 cream 0.15% or vehicle to psoriatic plaques that will not exceed an application area of 5% BSA. Assignment of drug or vehicle will be made at a 1:1:1 ratio according to a computer generated randomization list. Randomization will take place at Baseline after the patient has been found to be fully eligible for participation. A kit containing ten (10) tubes of study medication will be assigned to each subject. Each kit has a unique kit number (randomization number).

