3.2. Sample Size and Power

A sample size of 24 per arm (72 total) will provide 80% power to detect a difference of 23% in

AD-ST-33.04 Effective date: 30-Jun-2017

the mean percent change from baseline in TPSS x TPA (cm²) between the ARQ-151 cream and the matching vehicle arms, with a standard deviation for the change of 25%. This is based on a 1-way analysis of variance (ANOVA) at the $\alpha = 0.025$ significance level. With a 16% dropout rate, the sample size for the study has been increased to 84 subjects.

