6.1.4. Handling of Dropouts or Missing Data

Any subject who withdraws from the study may be replaced at the discretion of the Sponsor. For AEs, if severity or relationship to study drug is missing, then it will be treated as missing. In general, missing data will not be imputed, except as described in [Section 6.1.8](#).

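### At the stated 16% dropout, 84 subjects leave about 70.6, not the 72 behind the power statement; the effect on power is about one percentage point

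*Protocol*

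**What the plan says.** Protocol 9.1.1 (Determination of Sample Size) sets the base size: "A sample size of 24 per arm (72 total) will provide 80% power to detect a difference of 23" percentage points in the primary endpoint, "with a standard deviation for the change of 25" percentage points. It names the method: "This is based on a one-way analysis of variance (ANOVA) at the $\alpha = 0.025$ significance level". The allowance for loss follows: "With a 16% dropout rate, the sample size for the study would be increased to 84 subjects".

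SAP 3.2 (Sample Size and Power) carries the same figures and closes with: "With a 16% dropout rate, the sample size for the study has been increased to 84 subjects".

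Three other places bear on the point:

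- **Allocation.** Protocol 8.6: "Assignment of drug or vehicle will be made at a 1:1:1 ratio according to a computer generated randomization list". The Protocol synopsis gives 84 subjects for Cohort 2, so 28 per arm.
- **Sidedness.** Protocol 9.1: "P-values of less than 0.05 will be considered statistically significant based on a two-sided test unless otherwise specified".
- **Replacement.** SAP 6.1.4: "Any subject who withdraws from the study may be replaced at the discretion of the Sponsor".

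Neither document shows how 84 was obtained from 72 and 16%.

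**The concern.** A dropout rate is a fraction of the subjects enrolled. An enrolment target that allows for dropout should leave the base size once that fraction has been lost. Here it does not: 16% lost from 84 leaves fewer than 72.

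The sample size paragraph is the plan's only statement of how much loss the design can absorb, and the SAP repeats it unchanged. As written, it credits the design with tolerating 16% dropout at 24 per arm, when the true limit is nearer 14%. A reader who checks the sum will find that 72, 16% and 84 cannot all stand.

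**Working it through.** **Inputs.** Difference 23 and SD 25 percentage points, 24 per arm (72 total), α = 0.025 per comparison, 16% dropout and 84 enrolled (Protocol 9.1.1, SAP 3.2); two-sided testing (Protocol 9.1); three equal arms (Protocol 8.6).

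**Step 1: reproduce the base size.** The noncentrality parameter for one active arm against vehicle is δ / (SD × √(2/n)). At n = 24 this is 23 / (25 × √(2/24)) = 3.187. With two-sided α = 0.025, noncentral-t power is:

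- 80.5% with two-arm error degrees of freedom (2 × 24 − 2 = 46);
- 81.3% with the pooled error degrees of freedom of a three-arm ANOVA (3 × 24 − 3 = 69).

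The claim of 24 per arm for 80% power therefore reproduces.

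**Step 2: find where 84 comes from.**

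- 72 × 1.16 = 83.52, which rounds up to 84. Per arm, 24 × 1.16 = 27.84 rounds up to 28, and 3 × 28 = 84.
- 72 / (1 − 0.16) = 85.71, which rounds up to 86. Per arm, 24 / 0.84 = 28.57 rounds up to 29, and 3 × 29 = 87.

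Multiplication by 1.16 gives the stated total exactly; division by 0.84 does not. That the plan multiplied is an inference from this match.

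**Step 3: apply the stated dropout to the stated total.** This step does not depend on how 84 was reached.

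- Remaining: 84 × 0.84 = 70.56, or 70.56 / 3 = 23.52 per arm.
- Loss that 84 can absorb while keeping 72: (84 − 72) / 84 = 14.3%.
- Shortfall in enrolment against the stated aim: 86 − 84 = 2 subjects, or 87 − 84 = 3 with equal arms.

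**Step 4: cost in power.** At n = 23.52 the noncentrality parameter is 23 / (25 × √(2/23.52)) = 3.155.

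| Per arm | Two-arm df | Three-arm ANOVA df |
|---|---|---|
| 24 | 80.5% | 81.3% |
| 23.52 | 79.5% | 80.4% |

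The loss is about one percentage point on either basis.

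**The case against.** The strongest reply is that the power claim survives. The documents base their calculation on a one-way ANOVA, for which pooled three-arm degrees of freedom are the natural choice. On that basis, power at 16% dropout from 84 is 80.4%, still at the stated 80%. Only with two-arm degrees of freedom does it fall below, and then by half a point. This stands. A reader might infer from the shortfall that the trial is underpowered, or that more subjects must be enrolled. The documents do not support either reading.

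Second, dropout is not the same as loss from the analysis. The primary analysis is a mixed model for repeated measures on the mITT population, which requires only one post-baseline efficacy evaluation (Protocol 9.1.2 and 9.2.1; SAP 5 and 8.1). Subjects who leave after Week 1 still contribute data, so counting only those who remain is conservative. Neither document says that 72 means subjects evaluable at Week 4. This limits the practical effect, but it does not reconcile the sentence. A dropout allowance added to an ANOVA-based size has a purpose only if dropouts are counted as lost.

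Third, SAP 6.1.4 lets the sponsor replace subjects who withdraw, which could cover two or three. Replacement is discretionary and unquantified, and it plays no part in the stated calculation. It could make up the numbers in practice without making the sentence correct.

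Finally, the multiplication by 1.16 should not be reported as a fact about the plan. It is the likely explanation; the inconsistency does not depend on it.

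**Conclusion.** The stated total does not deliver 72 subjects at the stated dropout rate. At 16% loss, 84 becomes about 70.6 (23.5 per arm), and 72 is kept only if loss is at most 14.3%. Keeping 72 at 16% would take 86 subjects, or 87 in equal arms.

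Severity is minor. The gap is two to three subjects and about one point of power, which leaves power between 79.5% and 80.4%. These figures assume the plan's own difference and SD, two-sided α = 0.025, loss spread evenly over the arms, and no contribution from subjects who drop out. The last assumption is conservative for the planned mixed model. No endpoint, test, significance level or population definition depends on the 16%.

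**What to change.** Replace the dropout sentence in Protocol 9.1.1 and SAP 3.2 with:

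> 84 subjects (28 per arm) allow about 14% dropout while keeping 24 per arm (72 total); at 16% dropout about 23.5 per arm remain and power is about 79.5% to 80.4%.

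It would help to add that the lower figure uses two-arm degrees of freedom and the upper one three-arm ANOVA degrees of freedom.

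The cost is one sentence in each document and a slightly less favourable dropout allowance. Enrolment, randomization and analysis stay as they are. Raising the total to 86 or 87 would also reconcile the figures, but a gain of about one point of power does not call for it.

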9.1.2 Subjects to Analyze

Safety population will include all subjects who are enrolled and received at least one confirmed dose of study medication. This population will be defined separately for each cohort.

The Modified Intent-to-Treatment (mITT) population will include all subjects who are in the safety population for Cohort 2 with at least one post-baseline efficacy evaluation.

Per-Protocol (PP) Population will include all subjects who are in the safety population for Cohort 2, were at least 80% compliant with study medication, and showed no other serious deviations from the study protocol.

The PK population will include all subjects receiving the active drug with sufficient plasma concentrations of roflumilast to define a profile, as determined by the pharmacokineticist. This population will be defined separately for each cohort.

9.1.3 Interim Analysis

No interim efficacy analyses are planned.

9.1.4 Background and Demographic Characteristics

Descriptive statistics will be used to summarize demographic characteristics (age, sex, and race) and background characteristics for the enrolled subjects in Cohort 1 and the randomized subjects in Cohort 2. Past/coexistent medical history information and physical examination observations and vital signs information for all randomized subjects will be presented in a by-subject listing.

9.1.5 Study Medication Compliance

The number of doses received by each subject based on diary data will be summarized using summary statistics (mean, standard deviation [SD], median, minimum, and maximum), and categorically.

The amount of study medication received by each subject based on tube weight will be summarized by treatment using summary statistics (mean, SD, median, minimum, and maximum), and categorically.

9.2 Efficacy (Cohort 2)

Efficacy will be assessed for Cohort 2 only.

9.2.1 Primary Efficacy Endpoint

In the parallel group assessment (Cohort 2), the Primary Efficacy Endpoint will be the Difference in mean percent change from baseline at week 4 in TPSS x TPA between each dose concentration level of ARQ-151 cream and vehicle control. This will be assessed as a sum of up to 3 target plaques per subject.

The primary endpoint will be analyzed using a mixed model for repeated measures (MMRM), with center, treatment, study visit, and study visit-by-treatment interaction as fixed effects and baseline TPSS x TPA score as a covariate. An unstructured covariance structure will be used, unless the model does not converge; in that case, the appropriate covariance structure will be investigated. The Bonferroni method will be used to control for multiplicity, where the significance level for each of the two comparisons of active versus placebo is $\alpha=0.025$.

Descriptive statistics for absolute and percent change from baseline at Week 4 will be provided.

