8.2.1 Dose Selection

The ARQ-151 cream 0.5% dose concentration was selected because of the efficacy observed in the Snape, et al study described above ([Snape 2016](#)). [REDACTED]

The dose concentration of ARQ-151 cream 0.15% was selected to determine whether lower ARQ-151 cream doses are effective and whether systemic exposure is also reduced.

Cohort 1 will involve application of ARQ-151 cream 0.5% to 25 cm² of psoriatic plaque(s). It is well known that cutaneous disease states can alter drug permeability as compared to normal human skin. Since psoriatic skin is known to have different drug permeability characteristics than normal skin ([Tang-Liu 1999](#)), we do not believe there is anything to be gained by prior application of topical drug to normal human volunteers. [REDACTED]

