4.1. Introduction

Data processing, tabulation of descriptive statistics, calculation of inferential statistics, and graphical representations, except for PK parameter estimation, will be performed primarily using SAS (release 9.4 or higher). All PK parameter estimations will be performed using WinNonlin® version 6.4 or later. If the use of other software is warranted, the final statistical methodology report will detail what software was used for what purposes.

For purposes of this SAP, “treatment within cohort” is defined as enrolled subjects (“Overall”) for Cohort 1 and treatment group (“ARQ-151 0.5%,” “ARQ-151 0.15%,” and “Vehicle”) for Cohort 2. For background and efficacy summaries for Cohort 2, this will be the randomized (ie, planned) treatment group; for safety summaries, this will be the actual (ie, received) treatment group.

Where possible, data for both cohorts will be summarized in the same output.

Continuous (quantitative) variable summaries will include the number of subjects (n) with non-missing values, mean, standard deviation (SD), median, minimum, and maximum.

Categorical (qualitative) variable summaries will include the frequency and percentage of subjects who are in the particular category or each possible value. In general, the denominator for the percentage calculation will be based upon the total number of subjects in the study population for the treatment groups within cohort, unless otherwise specified.

The minimum and maximum will be reported with the same degree of precision (ie, the same number of decimal places) as the observed data. Measures of location (mean and median) will be reported to 1 degree of precision more than the observed data and measures of spread (SD) will be reported to 2 degrees of precision more than the observed data.

Percentages will be presented to 1 decimal place, unless otherwise specified.

Unless otherwise indicated, all statistical tests will be conducted at the 0.05 significance level using 2-tailed tests, and *p* values will be reported. Corresponding 95% confidence intervals (CIs) will be presented for statistical tests.

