6.1.3. Multiple Comparisons

The type I error rate of $\alpha = 0.05$ will be maintained for the entirety of the primary endpoint by using the Bonferroni method to control for multiplicity, where the significance level for each of the 2 comparisons of active versus placebo is $\alpha = 0.025$.

No adjustments will be made for multiple comparisons for other endpoints; all analyses will be conducted at the $\alpha = 0.05$ level.

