8.1. Primary Efficacy Analysis

The primary efficacy endpoint is difference in mean percent change from baseline at Week 4 in the product of TPSS x TPA between each dose concentration level of ARQ-151 cream and vehicle control. This will be assessed as a sum of up to 3 target plaques per subject.

The primary endpoint will be analyzed using a mixed model for repeated measures (MMRM), with center within country, treatment, study visit, and treatment-by-study visit interaction as fixed effects and baseline TPSS x TPA score as a covariate. In comparing the visit value to baseline within each treatment group, least squares (LS) mean percent change from baseline will be presented along with associated 95% confidence interval (CI). In comparing treatments (ARQ-151 minus Vehicle), LS mean differences in percent change from baseline will be presented along with associated 95% CI and pairwise treatment *P* value. An unstructured covariance structure will be used, unless the model does not converge; in that case, the appropriate covariance structure will be investigated. Possible covariance structures include autoregressive (AR [1]), compound symmetry (CS), and variance components (VC) with each model fit to find the covariance structure with the best fit. The fit statistics will be compared for all covariance structures; the structure with the smallest Akaike information criterion will be retained as the preferred model.

The Bonferroni method will be used to control for multiplicity, where the significance level for each of the 2 comparisons of active versus placebo is $\alpha = 0.025$.

Descriptive statistics for absolute and percent change from baseline at Week 4 will be presented by treatment group.

The primary efficacy analysis will be based on the mITT Population. This analysis will be repeated for the PP Population.

As a sensitivity analysis, the primary endpoint will be analyzed using an analysis of covariance (ANCOVA) with factors for center within country and treatment as fixed effects and baseline TPSS x TPA score as a covariate.

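### Optional: Holm in place of single-step Bonferroni keeps the 0.05 family-wise bound and adds about 4.5 points of per-dose power if both doses have the planned effect

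*Protocol*

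**What the plan says.** Protocol 9.2.1 tests each of the two concentrations against vehicle on percent change in TPSS x TPA at Week 4: "The Bonferroni method will be used to control for multiplicity", at 0.025 per comparison. SAP 6.1.3 gives the aim, that a type I error of 0.05 "will be maintained for the entirety of the primary endpoint by using the Bonferroni method to control for multiplicity". SAP 8.1 repeats the rule. Neither document mentions a step-down procedure.

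The sample size uses the same level. Protocol 9.1.1: "A sample size of 24 per arm (72 total) will provide 80% power to detect a difference of 23" percentage points, with an SD of 25. SAP 3.2 adds: "This is based on a 1-way analysis of variance (ANOVA) at the" 0.025 level.

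The intervals are set at a different level. SAP 4.1: "Corresponding 95% confidence intervals (CIs) will be presented for statistical tests". SAP 8.1, for active minus vehicle: "LS mean differences in percent change from baseline will be presented along with associated 95% CI".

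**The concern.** Single-step Bonferroni holds the second dose at 0.025 even after the first dose has succeeded. A family-wise bound of 0.05 does not require that. Protocol 8.2.1 says the 0.15% cream "was selected to determine whether lower ARQ-151 cream doses are effective" (and to see whether systemic exposure falls), so the result for each dose is a study question in itself. A valid procedure that rejects more often at no cost in sample size is worth considering.

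The second, smaller point is the interval level. A dose with p between 0.025 and 0.05 will have a 95% interval that excludes zero but will not be declared significant. The plan does not say how to read such a result.

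**Working it through.** **Inputs.** Difference 23, SD 25, 24 evaluable per arm, alpha 0.025 (Protocol 9.1.1, SAP 3.2); two-sided tests (Protocol 9.1, SAP 4.1); 1:1:1 allocation with one shared vehicle arm (Protocol 8.6); 84 randomized, so 28 per arm.

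**1. The plan's own power.** SE of a difference = 25 × √(2/24) = 7.217. Noncentrality = 23 / 7.217 = 3.187. By the noncentral t distribution at two-sided 0.025:
- two-sample test, 46 df, critical value 2.317: power 80.5%
- pooled ANOVA error, 69 df, critical value 2.291: power 81.3%

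The stated 80% holds.

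**2. Validity of Holm.** Test the smaller p-value at 0.025; only if it is significant, test the larger at 0.05.
- Both doses null: any rejection needs the smaller p ≤ 0.025, with probability at most 2 × 0.025 = 0.05.
- One dose null: rejecting it needs its own p ≤ 0.05, with probability at most 0.05.
- Any dose with p ≤ 0.025 is declared under both rules, so Holm never declares less. This does not depend on the model.

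**3. Power.** Simulation of three normal arms, SD 25, pooled variance on 3(n − 1) df, at least 2,000,000 trials per scenario; repeat runs agree to about 0.1 point. The documents give no separate effect for 0.15%, so the values 15, 11.5 and 0 are assumptions.

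| n per arm | True differences | Quantity | Bonferroni | Holm |
|---|---|---|---|---|
| 24 | 23, 23 | each dose | 81.3% | 85.8% |
| 24 | 23, 23 | both doses | 70.6% | 79.7% |
| 24 | 23, 23 | at least one | 91.9% | 91.9% |
| 24 | 23, 15 | weaker dose | 42.1% | 52.0% |
| 24 | 23, 11.5 | weaker dose | 24.9% | 34.0% |
| 24 | 23, 0 | null dose declared | 2.5% | 4.3% |
| 24 | 0, 0 | any false declaration | 4.6% | 4.6% |
| 28 | 23, 23 | each dose | 87.4% | 91.1% |
| 28 | 23, 0 | null dose declared | 2.5% | 4.5% |

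Arithmetic check: the two per-dose powers must sum to power for both plus power for at least one. Holm: 2 × 85.8 = 171.6 = 79.7 + 91.9. Bonferroni: 2 × 81.25 = 162.5 = 70.6 + 91.9.

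When the other dose is weaker, the 23-point dose itself gains only 1.3 points (other dose at 15), 0.5 (at 11.5) or about 0.2 (at 0).

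**4. Interval mismatch.** With an observed SD of 25 and 69 df, a 95% interval excludes zero once the observed difference passes 1.995 × 7.217 = 14.4, but significance at 0.025 needs 2.291 × 7.217 = 16.5. Share of trials, 24 per arm, with a 95% interval excluding zero for an undeclared dose:

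| True differences | Bonferroni | Holm |
|---|---|---|
| 23, 23 | 13.0% | 3.9% |
| 23, 15 | 17.7% | 6.5% |
| 23, 11.5 | 16.5% | 6.9% |
| 23, 0 | 9.2% | 7.3% |
| 0, 0 | 4.8% | 4.4% |

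Joint coverage of the two intervals is about 91.0% at the 95% level and 95.4% at 97.5%. If 97.5% intervals accompanied Holm, a dose declared only at the second step would have an interval that includes zero; at (23, 23) this happens in 13.0 − 3.9 = 9.1% of trials.

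**The case against.** There is no defect to correct. Bonferroni is stated the same way throughout, agrees with the sizing alpha, delivers the stated power and meets the only type I error aim in the documents. No passage sets a power target for both doses, and in this Phase 1/2a trial estimates, intervals and p-values appear for both doses whatever the rule. All of that stands, and it is why the point is only optional.

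The 4.5 points also belong to one setting. The gain is about 3.6 at 28 per arm, and 3.0 (24 per arm) or 2.0 (28 per arm) if covariate adjustment brought the residual SD down to an assumed 22. This stands too, although 4.5 is not a ceiling: a weaker second dose gains 9 to 10 points.

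Holm is also a trade-off, since it gives up the 0.025 protection for each dose. That is true, but the rate stays inside the 5% bound the SAP sets.

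Finally, the interval mismatch is weak support for Holm: Holm shrinks it when both doses work, barely changes it when one is null, and never removes it. The clean cure is 97.5% intervals with Bonferroni kept. This is correct, and the two matters should be decided separately.

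**Conclusion.** The point holds as an optional improvement. The planned test is valid and adequately powered. Holm would add about 4.5 points of power per dose and 9.1 points for both doses at the planning values, and nothing to the chance of at least one success. The cost is a false-declaration rate of about 4.3% instead of 2.5% for a null dose when the other works.

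These sizes rest on the plan's ANOVA sizing model with SD 25. The MMRM with center and baseline terms was not simulated, because the documents give no between-visit correlations, so they are approximate. Holm's 0.05 bound and the fact that it never rejects less need no such assumption. The mismatch between 0.025 tests and 95% intervals is a separate reporting matter that exists under the present plan.

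**What to change.** Choose one option and write it down before unblinding.

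- **Adopt Holm.** In Protocol 9.2.1 and SAP 6.1.3 and 8.1, test the smaller of the two primary p-values at 0.025 and, only if it is significant, the larger at 0.05. Keep the 95% intervals and state that they are not simultaneous. If 97.5% intervals are added, footnote that a dose declared only at the second step can have one that includes zero.
- **Keep Bonferroni.** This is defensible if exact agreement between test and interval, or the 0.025 protection per dose, is preferred. Report 97.5% intervals for the two primary comparisons, as an exception to SAP 4.1 and 8.1. The mismatch then disappears with no change of test.

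Cost: Holm needs wording in two SAP sections plus either an amendment of Protocol 9.2.1 or an entry in SAP Section 10; the interval option needs SAP wording only. The SAP is already Version 1.0, so either needs a revised version. On timing, Protocol 9.1 says: "The SAP will be finalized before the database is locked and unblinded for Cohort 2". Sample size, data collection and model do not change.
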